successful penile erection). Should the patient wish to participate, the informed consent process will occur in a private clinic room and the patient will be given as much time as necessary to read and reflect upon the informed consent and all questions will be answered. No study procedures will be done prior to obtaining informed consent.

Those who wish to participate will sign an informed consent and will become familiar with the scope and protocol of the study. They will fill out the erectile function component of the international index of erectile function (IIEF-5), Erection Hardness Scale (EHS), Erectile Dysfunction Inventory of Treatment Satisfaction (EDITS), and Treatment Satisfaction Scale (TSS) questionnaires as a baseline. Patients will then be provided with a new Viberec stimulator and the manual, and will subsequently be instructed on the proper use of the device. Patients will demonstrate device use to ensure clarity with the explanation and instructions.

Prospective data will be collected from study subjects who will use the Viberec device. Men will be asked to perform vibratory stimulation of the penis while focused on sexual/erotic thoughts for approximately 7-10 minutes (depending on erectile response) for at least 3 times each week, at least 24 hours apart, throughout a four-week period. Men can perform the stimulation once daily, as long as each session is more than 24 hours apart. Men will record the frequency of device use, erectile response with stimulation, and whether they were able to achieve sexual satisfaction, which may include self-stimulation or penetrative intercourse.

Participants will fill out the IIEF-5, EHS, EDITS, and TSS questionnaires on week 4. The answers to these validated questionnaires will be compared to baseline to evaluate patient effect when using the device. The diaries will be evaluated to explore both the safety, as well as the patient effect when using the Viberec device.

If study subjects decide to use PDE-5 inhibitors during the 4-week study period (not provided by investigators), we ask that they record frequency of use, time, drug type, dosage, and commentary of sexual response as a result separately.

b. Study duration and number of study visits required of research participants.

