The total duration of subject participation in this study is **4 weeks**. A total of 2 clinic visits will be included in this study. The first clinic visit will be the baseline evaluation and explanation of the study, and then a follow-up visit approximately 4 weeks after initiation of study period. This 4 week visit is standard of care visit, based on physician's discretion after starting a new therapeutic treatment of ED.

Initial visit: Perform the history and physical exam and to discuss the clinical study. Informed consent will be obtained at this visit if participant willing to proceed and meet inclusion criteria. Study subjects will fill out the IIEF-5, EHS, EDITS, and TSS for baseline documentation. Participants will receive their Viberec device, including the user manual (attached) and will receive instructions on the use of their device. Patients will do a brief demonstration of how to use the device in order to ensure patient understanding and proper utilization.

Follow up visit at four weeks: This is the standard follow-up appointment to discuss efficacy and

safety of the stimulator. The Vibrect device is the patient's to keep, however if they are not interested in continuing use, then can bring the device back and it will be returned to Reflexonic by the team. The patient will fill out the IIEF-5, EHS, EDITS, and TSS forms again and will be collected from the patient by nursing staff or the investigators. Patients will have a penile examination to document any sores, lesions, or irritation.

Patients in this study will not be blinded, as we would not be able to blind patients to using a vibratory device or not, and there is only one treatment group. Patients in this study will not be compared to a non-treatment group. This is a phase I trial exploring safety of the device, and we therefore want all participants to use the device and provide their individual reports and feedback.

The standard of care for men presenting with mild-to-moderate ED and requesting treatment are PDE5-inhibitors (Viagra, Levitra, Cialis). While on study, patients will be able to use on-demand PDE5-inhibitors as per usual. Future studies may compare Vibrect to PDE5-inhibitors, but the present study is exploring safety of the device.

Patients would be considered a treatment failure if they are unable to use the Vibrect device as recommended for the trial due to either mechanical issues or inability to tolerate the penile sensation when using the device.

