5. STUDY STATISTICS

a. *Primary outcome variable.*

The primary outcome parameter is safety, patient tolerability, and patient satisfaction with the hand-held penile vibratory system.

b. *Secondary outcome variables.*

The secondary outcome parameter is erectile response (erection, rigidity, orgasm) and subjective patient and/or partner sexual satisfaction, when applicable.

c. *Statistical plan including sample size justification and interim data analysis.*

This is a prospective study. Descriptive statistics will be performed based on pre-treatment and post-treatment responses to validated sexual function questionnaires. This data will be utilized to perform power analyses to generate future studies. We will recruit a total of **20 patients** for this study.

d. *Early stopping rules.*

Patients who stop the use of the Viberec early, will be recorded and their reasoning will be documented. Since this is a phase I trial, patient safety and satisfaction is the primary outcome and therefore it will be essential to understand why a patient stops use prematurely.

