6. RISKS

a. *Medical risks, listing all procedures, their major and minor risks and expected frequency.*

Definition of adverse events: Adverse events related to the use of the Viberec device include any user discomfort during or after use of the device, including pain, fatigue, numbness, rash, or device malfunction.

Potential (anticipated) adverse events

-Pain, numbness of the penis or the hand holding the device

Adverse event reporting

i. Description of adverse events (see risk analysis)

ii. Serious adverse events

-potential serious adverse events include device malfunction, vibrating pad dislodgment and vibrating tip damaging the penis.

iii. Unanticipated adverse device effects

- Device overheats and burns. The device will not be used while connected to the electric outlet, therefore minimizing potential risk of burns or overheat

iv. Adverse event severity/strength: To be reported immediately to senior investigator and principal investigator.

v. Serious adverse event narratives: reports and narratives will be included

b. *Time periods for adverse events reporting:*

Weekly reporting to senior and principal investigator.

Risk	Occurrence Potential	Mitigation
Inability to correctly use the Viberect device according to User's Guide.	Mild	Detailed and Simplistic (with figures) instructions are included in the in the User's Guide. Also the manufacturer recommends in the User's Manual that the user perform the Viberect method for at least two occasions in a clinical setting before using at home.
Any user discomfort during or after use of the device, including pain, fatigue, numbness, rash, device malfunction or hand pain from holding the device.		Viberect Device must not be used more than 10 minutes per day with strict accordance to the User's manual. Also, manual includes A WARNING that states: "Vibratory stimulation may cause a superficial trauma to the skin resulting in bruising, bleeding or superficial ulceration. If any such condition occurs, refrain from vibrating and consult your physician. This device should not be used over swollen or inflamed areas or skin eruptions."
User does not respond to device.		User's Guide provides direction that the Viberect may have to be used multiple times before it is effective. Not all men will responds to this treatment.

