There is no financial risk to the patient. The Viberect device will be provided for free to each participant. Clinic visits will be billed to the participant's insurance company as a consultation and a standard-of-care follow-up appointment. If the participant does not have insurance coverage for specialist appointments, they will be responsible for paying for their visits out-of-pocket. The study does not offer financial compensation, however the Viberect device will be provided for free to the participant.

Steps taken to minimize the risks.

A comprehensive user manual will be provided to each study subject, and detailed person

to person instructions will be given to them prior to enrolling in the study. A demonstration will be provided prior to the patient using the device independently to ensure they have a full understanding of how to use the device.

Plan for reporting adverse events unanticipated problems or study deviations.

The occurrence of any serious adverse effects will end the patient's participation in the study and halt enrollment in the study to determine the safety of continuing. Each and every possible adverse effect of Viberec will be investigated and treated individually to minimize the participant's discomfort. The safety of having the individual complete the study will also be assessed on an individual basis. At any time the participant can decide to terminate his participation in the study and no penalty or loss of benefits to which they are entitled.

7. Confidentiality

Paper consent forms, enrollment check sheets, and other source or study documentation will be kept in a study binder. This binder will be stored in a locked office available only to the study team. Electronic data will be housed in a secure password protected database maintained by the Data Informatics Services Core within the Johns Hopkins Biostatistics Center. Only the study team will have access to this secure database. To maintain the protected information of patients enrolled in this study, only the study Principal Investigator and primary coordinators will have the ability to export data containing identifying information from this master database. For the purposes of analysis, only de-identified data will be exported.

8. Benefits

i. Individual participant

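### The protocol ends study participation, not just device use, after a serious adverse effect, and does not say whether week-4 examination and satisfaction data are still collected

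*Protocol*

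**What the plan says.** Protocol section 5a defines the primary outcome: "The primary outcome parameter is safety, patient tolerability, and patient satisfaction with the hand-held penile vibratory system". Section 5c sets the size: "We will recruit a total of 20 patients for this study".

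Post-baseline study assessment is concentrated in one visit. Section 2 says "Participants will fill out the IIEF-5, EHS, EDITS, and TSS questionnaires on week 4", and the description of the four-week follow-up visit in 2b adds "Patients will have a penile examination to document any sores, lesions, or irritation". No other penile examination is scheduled after the device is handed out, and no early-termination visit is described. Section 2b calls the four-week visit standard of care, at the physician's discretion.

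Section 6, in the plan for reporting adverse events, says "The occurrence of any serious adverse effects will end the patient's participation in the study"; the same sentence also halts enrollment while safety is reviewed. The next sentence promises that every possible adverse effect will be looked into and treated case by case. The one after it says that the safety of the man completing the study is also judged individually.

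On which events are serious, section 6 says "potential serious adverse events include device malfunction, vibrating pad dislodgment and vibrating tip damaging the penis". On what is kept, it says "Serious adverse event narratives: reports and narratives will be included". Section 5d adds, for men who stop using the device, "Patients who stop the use of the Viberec early, will be recorded and their reasoning will be documented".

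**The concern.** In a safety study, stopping the device and stopping observation are different decisions. The section 6 rule is written about participation in the study, so it makes both at once. The men it removes bear most directly on the primary outcome, and they are removed because of that outcome. Data missing for this reason cannot be treated as missing by chance.

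Two things are at stake. First, for a man with a serious event, the study may hold no planned record of the penile findings at week 4. Secondly, his EDITS and TSS would be absent, so satisfaction would be summarised only in men for whom nothing serious went wrong. The second effect may be wider than it looks, because device malfunction is on the list of potential serious events. Section 2b treats men who cannot use the device for mechanical reasons as treatment failures, so their views on satisfaction matter.

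**Working it through.** The plan gives no figure to reproduce here. The check is a comparison of the text, followed by simple bounds.

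**Text, side by side**

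| Item | For a man removed after a serious event | Where |
|---|---|---|
| The event | Kept: report and narrative | Section 6 |
| Care for the event | Provided, case by case | Section 6 |
| Week-4 penile examination as study data | Not provided for once participation ends | Sections 2b and 6 |
| Week-4 IIEF-5, EHS, EDITS, TSS | Not provided for once participation ends | Sections 2 and 6 |
| Status of the event at week 4 | Not specified; contents of the narrative are not defined | Section 6 |

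The sentence on individual judgement can be read in two ways. If it covers only non-serious effects, the automatic end of participation stands and the gaps in the table follow. If it also covers serious effects, it conflicts with the automatic rule. Either way the paragraph needs reconciling.

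Device malfunction has the same kind of ambiguity. Section 6 names it in the general definition of adverse events and again among potential serious ones, so it is unclear whether a malfunction without injury triggers removal.

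The SAP does not fill the gap. Its mixed model for missing time points applies to questionnaire scores, not to the examination. It normally relies on data being missing at random, which is doubtful when a man has only a baseline score because of the event.

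**Size**

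Input: n = 20 (section 5c). Let k men be removed and x of the remaining 20 − k have some week-4 finding.

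- Observed proportion: x / (20 − k).
- All-20 proportion: between x/20 and (x + k)/20.
- Largest possible gap: k/20, reached at x = 0 or x = 20 − k.

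For k = 1 the gap is up to 1/20 = 5 points (19/19 = 100% satisfied against 19/20 = 95% if the removed man is not). For k = 2 it is up to 2/20 = 10 points (18/18 = 100% against 18/20 = 90%).

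The documents give no serious-event rate. For assumed per-man rates p, and all 20 men enrolled, the chance of at least one serious event is 1 − (1 − p)^20:

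| Assumed p | Chance of at least one | Expected number (20p) |
|---|---|---|
| 1% | 18% | 0.2 |
| 2% | 33% | 0.4 |
| 5% | 64% | 1.0 |
| 10% | 88% | 2.0 |

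The problem may therefore never arise, or may affect one or two men. At this sample size, one or two men are visible in the results.

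**The case against.** The strongest reply is that the primary safety outcome does not lose these men. Serious events go immediately to the investigators, with reports and narratives, and the diaries are also evaluated for safety. The week-4 visit is standard of care, so a removed man may well be seen anyway. The sentence on individual judgement suggests that removal may not be automatic. All of this stands, and it limits the point to week-4 status and scores. It does not close the gap, because nothing makes a standard-of-care visit study data once participation has ended.

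Three stronger readings are tempting, and the documents do not support them.

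- A reader might infer that the worst safety events disappear from the study. They do not; the reports and narratives keep them.
- A reader might infer a large downward bias in lesion rates. Suppose, as assumed counts, that two men are removed for penile injury and one lesion is found in the other 18. The examination alone gives 1/18 = 5.6%, against up to 3/20 = 15% if both injuries persist. But those two injuries are already in the event reports, so reports and examination together identify 3 of 20 men. The contrast holds only if the examination is read alone, and neither document defines a week-4 lesion rate as an estimate. Two removals with all 20 enrolled would also require enrollment to be complete already or to have resumed after the halt.
- A reader might infer that men who merely stop using the device are lost too. Section 5d requires the stop and its reason to be recorded; it does not take these men out of the week-4 visit.

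**Conclusion.** The point holds in a limited form and is worth correcting. Section 6 ends study participation after any serious adverse effect without saying what happens to data collection, and it sits uneasily with the sentence on individual judgement in the same paragraph. On the literal reading, the week-4 examination and the satisfaction scores are missing because of the event, and week-4 summaries describe only men without one. The effect is at most 5 percentage points of a week-4 proportion per man removed.

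This rests on two assumptions: that the automatic rule is applied as written, and that a clinical visit after removal is not otherwise captured as study data. No sentence in the documents says that the data are discarded; the conclusion follows from the rule combined with the absence of any follow-up provision.

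**What to change.** Reconcile the two sentences in section 6, and state separately what happens to device use and what happens to data collection. The rule on device use stays with the sponsor. For data collection, state that:

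- unless he withdraws consent, a man whose device use ends after a serious event attends the week-4 visit already planned;
- his penile examination and questionnaires at that visit count as study data;
- the status of the event at that visit is recorded;
- safety is reported with all men given a device as the denominator, combining event reports and examination findings.

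It would also help to say whether a device malfunction without injury counts as serious.

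The cost is a wording change that adds no visit or procedure. Some removed men may decline to return, and under section 6 the visit is billed to insurance or paid by the man, as in usual care. Open-ended follow-up of events is not needed for this fix and would go beyond the four-week, two-visit schedule.

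If data collection has finished, as the SAP's past tense suggests, the report can still give the number of men removed, their week-4 status where known, and each week-4 result over both the men assessed and all men given a device.

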COVER PAGE

NCT number: 01715571

Official Title: Assessment of Penile Vibratory Stimulation
Using the Viberect in Men with Mild-Moderate ED

Document date: 5/7/2021

Principal Investigator: [name]

Participating Site: Johns Hopkins University, Baltimore,
MD, USA

Statistical Analysis Plan (SAP)

This was a pilot study and there were no data to suggest the magnitude of the effect of Viberect on ED, we performed power calculations for various scenarios of change in IIEF. The scenarios used a pattern of means with an absolute increase from pre-treatment to 4 weeks of 4 units for IIEF, and plausible conservative (higher than expected) values for the within-subject standard deviation that were increased until power fell below 80%. For IIEF, we evaluated power if the pre-treatment mean was the midpoint of the range of values eligible for study: IIEF = 18 (range 11-25). However, the power was not sensitive to the pre-treatment mean, and showed little variation according to the specific changes in mean score between time points, for a fixed overall change from pre-treatment to 4 weeks. The table below shows power to detect a 4 unit increase in IIEF with 20 patients evaluated at 4 time points, $\alpha = 0.05$, within-subject standard deviation and autocorrelation both constant over time. Power calculations were performed using PASS v. 11 (NCSS Software, Inc., Kaysville, UT), according to the method of Mueller (Mueller 1989).

Pattern of means over 4 time points		Within-subject SD	Power
Pre-test	4 weeks		
IIEF			
18	20	2	>0.99
18	20	3.5	0.88
18	20	3.8	0.81

Thus, despite the small size of the study, power is likely to be more than adequate to detect the minimum changes in IIEF (increase 4 units) considered clinically relevant.

Should a measurable positive effect be noted, a more extensive randomized, placebo controlled, blinded and possibly multi-institutional trial be considered. The information obtained from the pilot study a help guide future studies if appropriate.

Pre-treatment IIEF, EHS, EDITS, and TSS scores was planning to be compared to post-treatment scores at 4 weeks. The primary analysis for all scores were repeated measures analysis of variance (RM ANOVA); if there are no missing time points, otherwise, a mixed model was used. The primary endpoint was the TIME effect, i.e. to test for a change from pre-treatment value of IIEF, EHS, EDITS, or TSS. The minimum change considered clinically relevant was an increase in IIEF and EDITS of 4 units and EDITS of 4 units. In addition to absolute change in IIEF or EDITS scores, we evaluated models of percentage change from pre-treatment value. If the overall effect of TIME is statistically significant, we used paired t-tests comparing pre-treatment to

each of the post-treatment values, with a Bonferroni p-value adjustment, to determine the time at which an increase in IIEF and EDITS of at least 4 points can first be detected. Covariates to be evaluated as potential confounding factors include age, comorbidity or cause of ED, body mass index, and other medications.

Data were analyzed using GraphPad Prism ver. 8 (GraphPad Software, San Diego, CA, USA). A P value $<.05$ was considered statistically significant.

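### The SAP's power table is for four time points, but IIEF is measured twice; two-visit power for 4 units is at least 0.93 and 0.88, not 0.88 and 0.81, with 20 completers

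*SAP*

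**What the plan says.** **SAP, power paragraph and table.** The target is a 4-unit rise: "The scenarios used a pattern of means with an absolute increase from pre-treatment to 4 weeks of 4 units for IIEF". The table is introduced with "The table below shows power to detect a 4 unit increase in IIEF with 20 patients evaluated at 4 time points", at alpha 0.05, with "within-subject standard deviation and autocorrelation both constant over time". Its header refers to a pattern of means over four time points, but only two mean columns appear, for pre-test and 4 weeks. All three rows print 18 and 20. The powers are >0.99 (SD 2), 0.88 (SD 3.5) and 0.81 (SD 3.8). The paragraph concludes that "power is likely to be more than adequate to detect the minimum changes in IIEF (increase 4 units) considered clinically relevant".

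**SAP, analysis paragraph.** Pre-treatment "scores was planning to be compared to post-treatment scores at 4 weeks". The TIME effect in a repeated measures ANOVA is the primary test. If it is significant, Bonferroni-adjusted paired t-tests at each post-treatment value are to find when a 4-point rise is first detectable.

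**Protocol, section 2 (Study Procedures).** "A total of 2 clinic visits will be included in this study". The questionnaires are completed at the first visit as baseline, and then: "Participants will fill out the IIEF-5, EHS, EDITS, and TSS questionnaires on week 4".

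**Protocol, section 5c.** "Descriptive statistics will be performed based on pre-treatment and post-treatment responses to validated sexual function questionnaires". Twenty patients are to be recruited; no power calculation is given for that number.

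**The concern.** The power paragraph and the schedule describe different designs. Four IIEF assessments lead to a test of TIME on 3 and 57 degrees of freedom. Two assessments lead to a test on 1 and 19, which is the paired t-test. The two have different power for the same 4-unit rise and the same SD, so the table cannot stand as the power of the week-4 comparison.

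Two further features make the table hard to check. The printed means differ by 2 units while the text says 4. The autocorrelation is called constant but has no value, and the SAP does not say whether the within-subject SD is the residual SD or the total SD at a visit.

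What is at stake is the accuracy of the only power statement in either document.

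**Working it through.** **Inputs.** n = 20; alpha = 0.05; rise = 4 units; SD = 2, 3.5, 3.8; four time points (all from the SAP power paragraph). Actual IIEF assessments: 2 (protocol, section 2). The documents give neither a correlation nor a dropout figure.

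**Formula.** For k visits with means m_j and residual SD s, the noncentrality is λ = n × Σ(m_j − mean)² / s². Power is the probability that a noncentral F on (k−1) and (k−1)(n−1) degrees of freedom exceeds its 5% critical value.

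**Step 1. Reproduce the printed powers: four visits, 4 units, residual SD.**
- Even rise (18, 19.33, 20.67, 22): Σ = 8.889. At SD 3.5, λ = 20 × 8.889 / 12.25 = 14.51 and power is 0.885. At SD 3.8, λ = 20 × 8.889 / 14.44 = 12.31 and power is 0.823.
- Near-even rise (18, 20, 21, 22): Σ = 8.75. λ = 14.29 and 12.12; power is 0.880 and 0.816.
- At SD 2 both exceed 0.99.

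These lie within about 0.01 of the printed 0.88 and 0.81. The match depends on the rise being even or nearly so: at SD 3.5, means of 18, 20, 20, 22 give 0.847 and 18, 18, 22, 22 give 0.992.

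**Step 2. The trial's own comparison: two visits, 18 to 22.** Here Σ = 2² + 2² = 8, on 1 and 19 degrees of freedom. This equals a two-sided paired t-test with SD of change = s√2.

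| Residual SD | SD of change | λ = 160/s² | Power | SAP prints |
|---|---|---|---|---|
| 2 | 2.83 | 40.0 | >0.99 | >0.99 |
| 3.5 | 4.95 | 13.06 | 0.929 | 0.88 |
| 3.8 | 5.37 | 11.08 | 0.884 | 0.81 |

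Power for 4 units falls to 80% at SD 4.28 (SD of change 4.28 × √2 = 6.06).

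**Step 3. If the SD is the total SD at a visit.** SD of change is s√(2(1−ρ)). Assumed values of ρ, at SD 3.5 and 3.8:
- ρ = 0: as in step 2.
- ρ = 0.3: SD of change 4.14 and 4.50; power 0.98 and 0.96.
- ρ = 0.5: SD of change 3.50 and 3.80; power 0.998 and 0.994.

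**Step 4. Sensitivity to completers (assumed numbers, residual SD or ρ = 0, SD 3.5 and 3.8).** 19 give 0.91 and 0.87; 18 give 0.90 and 0.85 (0.845 before rounding); 17 give 0.88 and 0.82. So the gap from the printed values closes at about 17 completers.

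**Step 5. The printed means taken literally: 18 to 20, two visits, 20 completers.** Residual SD or ρ = 0: 0.85, 0.40 and 0.35 at SD 2, 3.5 and 3.8. Total SD with ρ = 0.5: 0.68 and 0.61 at SD 3.5 and 3.8.

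**The case against.** The strongest reply is that nothing turns on this. With 20 completers the correct power is higher than printed, so the table errs on the safe side. The protocol's primary outcome is safety, tolerability and satisfaction (section 5a), and section 5c does not derive 20 patients from this table. All of that stands. It limits the point to a correction of the record, but it does not make the printed figures the power of the planned comparison.

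Three stronger readings are tempting, and the documents do not support them.

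- **That the study was planned for 2 units and is underpowered (0.40 and 0.35).** The SAP's prose states 4 units repeatedly, and the analysis paragraph gives 4 as the minimum relevant change in IIEF. A header for four time points above two mean columns suggests that intermediate columns may have been lost; 18 and 20 are also the first two values of 18, 20, 21, 22, which fits the powers. That is inference, but enough not to treat 2 units as the intended effect.
- **That the origin of the powers is unknowable.** Other combinations do match, for example two visits, 18 to 20, with ρ = 0.7 (0.879 and 0.822). They need a 2-unit rise that the prose contradicts and a correlation chosen to fit. The design the SAP states in words comes close with no such tuning.
- **That a follow-on trial would be mis-sized.** Protocol section 5c says future power analyses will use this study's own data, and the SAP says that information obtained from the pilot may guide later work. Neither relies on this table.

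The Bonferroni wording is harmless: with one post-treatment value there is one test and a multiplier of 1.

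**Conclusion.** The point holds as an error in the stated power. The printed >0.99, 0.88 and 0.81 belong to a four-visit ANOVA that the schedule does not provide for. For the baseline to week-4 comparison, power for 4 units is >0.99, 0.93 and 0.88, so the table understates it by about 0.05 at SD 3.5 and 0.07 at SD 3.8.

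This rests on 20 completers, two-sided 0.05, and the SD being residual (or ρ = 0). The figures 0.93 and 0.88 should not be quoted without those conditions: positive correlation with a total SD raises them, and fewer completers lower them. The SAP's conclusion of adequate power for 4 units survives. The mismatch between the printed 2 units and the stated 4 is a second, separate fault in the table, of uncertain cause.

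**What to change.** Replace the table with power for the paired baseline to week-4 comparison: means 18 to 22, 20 completers, two-sided 0.05, stated by SD of change.

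| SD of change | Power |
|---|---|
| 2.83 | >0.99 |
| 4.95 | 0.93 |
| 5.37 | 0.88 |

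Say whether the within-subject SD is residual or total and, if total, give the correlation used. Delete the reference to four time points from the text and the table header. Any line for fewer completers (for example 17: 0.88 and 0.82 in the last two rows) should be labelled an assumption, because the documents give no dropout figure.

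As tidying only:
- In the SAP analysis paragraph, drop the redundant Bonferroni wording and the search for the first time of detection.
- Reconcile the eligible IIEF range, which is 11 to 25 in the SAP and 13 to below 25 in protocol section 3.
- Describe 18 as an assumed baseline mean. It is the midpoint of 11 to 25, since (11 + 25)/2 = 18, but not of whole-number scores from 13 to 24, since (13 + 24)/2 = 18.5. The power does not depend on it.

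The cost is one recalculated table and some SAP wording. No patients, visits or data are added, and the week-4 comparison is unchanged.
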